#### Endorail Solution Syringe (ESS)

ESS included in the Endorail Set is disposable and intended for single use. The syringe is pre-filled with a hypertonic water-based saline solution with high sodium citrate and sodium chloride concentrations.

#### Endorail Powder (EP)

Endorail Powder is a 50 mL vial containing dry carbonyl iron powder.

#### Spike

The spike is a tool required for piercing the vial and inject the saline solution in the vial.

#### Endorail Ferromagnetic Fluid Syringe (EFFS)

Before using Endorail the saline solution contained in the syringe need to be mixed with the iron powder. For this purpose, the ESS is connected with the spike and the spike is connected with EP. After that the saline solution has been mixed with the iron powder, at the end of the preparation phase, the syringe is filled with a water dispersion of iron micrometric particles called Endorail

Ferromagnetic Fluid.

#### Endorail Handpiece (EH)

Endorail handpiece (EH) contains a powerful permanent magnet. The handpiece is reusable and allows both the safe use of the magnet and the regulation of the magnetic field exerted on the filled balloon. EH is used during the procedure to magnetically anchor the balloon filled with ferromagnetic fluid.

Thanks to a screw-like mechanism the magnet can be moved inside the handle. There are 5 different magnet positions that correspond to 5 different levels of magnetic field intensity. The first level is the weakest and is called MIN Level. The fifth level is the most powerful one and also the most dangerous. For safety reasons EH should be always used and stored carefully following the instruction for use. EH misuse can cause severe adverse events both for patients and users. The magnetic field can interfere with other ferromagnetic objects or electronic devices.

#### Endorail Cart (EC)

Endorail Cart is used for the storage and transportation of Endorail Handpiece. It is composed by a case and a base with wheels. The case is provided with a shield for magnetic fields to avoid accidental interferences between the magnet and other ferromagnetic objects or electronic devices.

## **5.2 Experimental Intervention (treatment/medical device)**

Endorail is a colonoscopy add-on device developed to be used without any modification to colonoscopes. Endorail is an accessory to an endoscope and is intended to facilitate positioning of a standard colonoscope during endoscopy of the large intestine. Endorail works as a magnetic anchor that is able to guide the colonoscope and to straighten colon curves and loops.

**In case caecal intubation time is longer than 10 minutes**, the balloon is inserted in the endoscope tool channel, advanced beyond the colonoscope tip and filled with 25 mL of biocompatible Endorail Ferromagnetic Fluid. The operator manually performs and controls the inflation and deflation of the balloon through the syringe. Thus, by applying the Endorail Handpiece over the patient abdomen, the balloon can be magnetically anchored. The magnetic power level can be increased by the operator according to the patient's body mass index and the successful anchorage of the balloon can be visually verified by the operator through the endoscopic images.

For achieving the optimal effectiveness, anchorage should be performed in any colon segments proximal to the sigmoid colon (descending colon, transverse colon, ascending colon, caecum and colon curves).

The anchored balloon guide allows to straighten the scope and thus the colon itself. As the balloon guide is kept in tension, its rigidity increases and works as a rail supporting the movements of the colonoscope. The guided colonoscope can thus be easily moved back and forward to allow better colonoscope positioning and colonoscopy completion.

The Endorail Balloon Guide pulled against the colonic wall by the handpiece magnetic field works as a distal anchor towards which the endoscope tip is advanced and the Endorail Balloon Guide inflation tube serves as a guide wire that leads the endoscope as it is pushed towards the magnetically anchored balloon. After the Endorail is removed, the straightened colonoscope can be easily pushed forward to achieve colonoscopy completion as foreseen in standard endoscopic technique.

The Endorail Balloon Guide does not affect the endoscope's flexibility, its field of view and the manoeuvrability of the endoscope's tip, nor does it limit the use of any standard endoscopy tools such as biopsy forceps, snare, needle etc. The Endorail Balloon Guide can be pulled back at any time during the procedure in order to allow the use of other endoscopic accessories.

EBG is a disposable device however it can be used up to three times in the same patient. For detailed description of the procedure, see the instruction for use of Endorail Set and Endorail System.

#### **5.2.1 Treatment with the investigational device**

Each procedure is performed by an experienced endoscopist. If possible, the entire procedure will be video recorded. Sedation will be performed by an anaesthesiologist or an endoscopist according to standard of care.

A standard colonoscope with instrument channel diameter bigger or equal than 3.7 mm will be used for colonoscopy.

Endorail will be used only in case caecal intubation time is longer than 10 minutes. For detailed description of the device and the procedure, see the instruction for use.

#### **5.2.2 Control Intervention (Clinical Practice)**

This clinical trial has no prospective control group; results about primary endpoints for efficacy and safety will be compared with the standard clinical practice and international guidelines reference values (Section 1.6).

#### **5.2.3 Packaging, Labelling and Supply**

The investigational medical device Endorail Set and Endorail System are produced and packaged by Endostart s.r.l., [name]. Endostart s.r.l. will also supply the investigational medical devices to the investigational study sites.

The labelling of the investigational device Endorail will be performed by Endostart s.r.l. in accordance with the ISO 14155 guideline for medical devices and to all the local requirements.

#### **5.2.4 Handling**

The Principal Investigator will be responsible for the correct storage and use of the investigational medical devices, as well as of its accountability (usage and returning). The site staff can be delegated by the Principal Investigator to the abovementioned activities.

The Sponsor of the study will be responsible for the distribution of the investigational medical devices to the site involved in the investigation.

At the end of the investigation, the unused investigational medical devices will be returned to the Sponsor for reconciliation.

#### **5.2.5 Storage Conditions**

No specific storage conditions are required for the use of the investigational medical device Endorail, which should be stored at room temperature.

### 5.3 Administration of experimental and control interventions

#### 5.3.1 Experimental Intervention

Endorail is a colonoscopy add-on device developed to be used without any modification to colonoscopes. Endorail is an accessory to an endoscope and is intended to facilitate positioning of a standard colonoscope during endoscopy of the large intestine. Endorail works as a magnetic anchor that is able to guide the colonoscope and to straighten colon curves and loops.

The procedure can be summarised according to the following description.

In case caecal intubation time is longer than 10 minutes, the balloon is inserted in the endoscope tool channel, advanced beyond the colonoscope tip and filled with 25 mL of biocompatible Endorail Ferromagnetic Fluid. The operator manually performs and controls the inflation and deflation of the balloon through the syringe. Thus, by applying the Endorail Handpiece over the patient abdomen, the balloon can be magnetically anchored. The magnetic power level can be increased by the operator according to the patient's body mass index and the successful anchorage of the balloon can be visually verified by the operator through the endoscopic images.

For achieving the optimal effectiveness, anchorage should be performed in any colon segments proximal to the sigmoid colon (descending colon, transverse colon, ascending colon, caecum and colon curves).

The anchored balloon guide allows to straighten the scope and thus the colon itself. As the balloon guide is kept in tension, its rigidity increases and works as a rail supporting the movements of the colonoscope. The guided colonoscope can thus be easily moved back and forward to allow better colonoscope positioning and colonoscopy completion.

The Endorail Balloon Guide pulled against the colonic wall by the handpiece magnetic field works as a distal anchor towards which the endoscope tip is advanced and the Endorail Balloon Guide inflation tube serves as a guide wire that leads the endoscope as it is pushed towards the magnetically anchored balloon. After the Endorail is removed, the straightened colonoscope can be easily pushed forward to achieve colonoscopy completion as foreseen in standard endoscopic technique.

The Endorail Balloon Guide does not affect the endoscope's flexibility, its field of view and the manoeuvrability of the endoscope's tip, nor does it limit the use of any standard endoscopy tools such as biopsy forceps, snare, needle etc. The Endorail Balloon Guide can be pulled back at any time during the procedure in order to allow the use of other endoscopic accessories.

EBG is a disposable device however it can be used up to three times in the same patient. For detailed description of the procedure, see the instruction for use of Endorail Set and Endorail System.

#### 5.3.2 Compliance with study intervention

Each enrolled patient will be contacted by telephone (V2, see **Section 6.2.2**) 7 days after the procedure to evaluate the occurrence of general and specific adverse events from the previous visit. To improve the adherence to the follow up, the investigator will recommend the commitment of each participant in concluding the study schedule.

In case the patient does not respond at the scheduled phone visit, a second attempt should be tried one week after V2 and, in case he/she is still untraceable, he/she will be re-contacted two weeks

---

after V2. In case the contact is still unsuccessful, the patient will be defined as lost to follow up as indicated in Section 5.5.

#### **5.4 Data Collection and Follow-up for withdrawn participants**

If study intervention is permanently discontinued, the participant will remain in the study to be evaluated for the efficacy and safety of the patient following Endorail procedure up to 7 days after the discontinuation, except in the case of participant death.

If a patient decides to withdraw the informed consent, this process will happen through a specific communication from the patient to the medical doctor; the physician will report the patient decision in the medical record. If the patient decides to withdraw before the procedure completion, no other data will be collected. If the patient decides to withdraw after the procedure, only the safety and efficacy information will be collected to evaluate the safety of the patient following Endorail procedure, up to 7 days after the colonoscopy.

Upon withdrawal of consent, the patient can:

- request that his/her previously collected data are deleted

OR

- accept the retention of the data collected up to the moment of withdrawal.

Since the withdrawal of consent is communicated to the investigator, it will be the investigator who will register the withdrawal in eCRF specifying whether to delete or not all the previously collected data. Moreover, as far as possible, the Investigator will complete the End of Study Visit eCRF page. The Investigator should try to ascertain the reason(s) for withdrawal while fully respecting the patient's rights.

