#### **4.5 Criteria for withdrawal / discontinuation of participants**

Patients have the right to withdraw from the investigation at any time for any reason including personal reasons (consent withdrawal). The Investigator also has the right to withdraw any patient from the investigation if he/she deems this appropriate and in the best interest of the patients.

Possible reasons to discontinue a patient from the study include:

- Patients' withdrawal of consent for study participation;
- Adverse events (AEs): occurrence of unexpected symptoms during the study, whose intensity or specific treatments require the discontinuation of the colonoscopy with the investigational product. The reason of discontinuation must be recorded in the medical records and in the eCRF. If necessary, patients will be given an appropriate symptomatic treatment that will be recorded in the medical records and in the eCRF, together with the outcome and the duration of the AE. In case of serious adverse reactions to the investigational device, the study sponsor must be advised within 24 hours and all procedures for the reporting of serious adverse events (SAEs) will be made effective;

- Protocol violation: at least one of the conditions that represent any of the exclusion criteria (refer to Section 4.3). The reason of discontinuation must be recorded in the medical records and in the eCRF;
- The Investigator considers the study procedure discontinuation as appropriate, in the best interest of the patient;
- The Sponsor will terminate the study for any reason (refer to Section 4.6);
- Patient dies during the study: the reason and the date of death will have to be recorded in the medical records and in the eCRF, together with the Investigator's opinion on the correlation between the cause of death and the investigational product.

Should a patient decide to withdraw from the study, all efforts will be made to complete and report the observations as thoroughly as possible. A complete final evaluation at the time of the withdrawal (study end-point) should be performed, and a clear, univocal explanation of the reason why the subject is withdrawn from the study should be reported in the medical record.

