#### **4.7 Replacements**

Patients who withdraw the informed consent before the completion of the procedure can be replaced by newly recruited patients. Similarly, for patients who are found to be lost to follow-up following the procedure completion and therefore cannot be reached by phone for the scheduled follow-up visit (Visit 2) a second and third attempt should be made after the second and third week; if the patient is still untraceable it can also be replaced by newly recruited patients (See section 5.5).

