### 7.2.4 Reporting of (Serious) Adverse Events and other safety related events

All SAEs/SADEs and DDs that could have led to a serious adverse device effect must be reported, whether or not considered causally related to the medical device, or to the study procedure(s). All the above-mentioned events will be recorded in the eCRF no later than 24 hours after acknowledging the occurrence of the event. If the eCRF system is not available, the paper SAE/DD/Device Incidents reporting form will be filled in (in English language, written in clear capital letters) and must be sent via email to the Sponsor at the email address indicated below.

Day 0 is the day the Investigator becomes aware of an event occurred to the subject, and it is used by the Sponsor as reference day for regulatory purposes. Each SAE and SADE must be tracked and assessed by the Sponsor. The Sponsor will report any SAEs/SADEs to the relevant Independent Ethics Committee (IEC) as required by local requirements of the committee and to the Competent Authority. The Sponsor will determine whether a SADE is considered “anticipated” or not. Each DD must be tracked and assessed by the Sponsor. Any DD that might have led to a SAE if suitable action had not been taken or intervention had not been made or if circumstances had been less fortunate will be reported to the Competent Authority.

All SAE/DD/Device Incidents, independently of their causal relationship, must be reported immediately (within 24 hours) in the eCRF SAE form; if the eCRF system is not available, the paper reporting form must be reported immediately (within 24 hours from awareness) via email or Certified Electronic Mail by the Investigator or his delegated to:

[name], Endostart s.r.l., [name].

[contact]

Certified Electronic Mail: [[contact]](mailto:[contact])

Email: [[contact]](mailto:[contact]) and [[contact]](mailto:[contact])

Initial notification should include:

- Identification of the Principal Investigator: name, address, study center, telephone number;
- Study protocol number;
- Subject's identification (ID number in the study, date of birth, sex, relevant medical history);
- Device name or code, beginning and end of treatment;
- Description of event and its onset;
- Measures undertaken to treat it;
- Opinion of the Investigator about the relation of the event to the tested medical device.

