### 9.1 Data handling and record keeping / archiving

Records and documents, including signed ICFs, pertaining to the conduct of this study must be retained by the investigator for 25 years after study completion unless local regulations or institutional policies require a longer retention period. No records may be destroyed during the retention period without the written approval of the sponsor. No records may be transferred to another location or party without written notification to the sponsor.

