### **9.1.3 Record keeping / archiving**

All study data must be archived for a minimum of 25 years after study termination or premature termination of the clinical trial.

Records and documents, including signed ICFs, pertaining to the conduct of this study must be retained by the investigator for 25 years after study completion unless local regulations or institutional policies require a longer retention period.

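### Section 5.4 allows all data of a treated patient who withdraws to be deleted, and section 8 does not say how that patient is counted

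*Combined protocol and SAP*

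**What the plan says.** Section 5.4 gives a patient who withdraws consent two options: to accept that data collected so far are kept, or to "request that his/her previously collected data are deleted". The investigator registers the withdrawal in the eCRF, "specifying whether to delete or not all the previously collected data". The choice is not confined to withdrawal before the procedure, and no data item is exempt.

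Other text points the other way:

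- Section 5.4 itself: "If the patient decides to withdraw after the procedure, only the safety and efficacy information will be collected", for up to 7 days after the colonoscopy.
- Section 4.5: on withdrawal, "all efforts will be made to complete and report the observations as thoroughly as possible".
- Section 7.2.4: "All SAEs/SADEs and DDs that could have led to a serious adverse device effect must be reported".
- Section 9.1: "No records may be destroyed during the retention period without the written approval of the sponsor".
- Section 9.1.3: "All study data must be archived for a minimum of 25 years after study termination or premature termination of the clinical trial".

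On the analysis side, 8.4.1 defines the ITT population as enrolled patients in whom Endorail was started. Section 8.5 says only that missing data are not replaced. Neither mentions a treated patient whose data have been deleted.

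**The concern.** Completion is recorded at the end of the colonoscopy (6.1.1, 6.2.1), and intra-procedure events are recorded at the same visit. A deletion request made afterwards therefore removes an outcome that has already been observed. The trial has one arm and is open-label, so the investigator who registers the deletion knows the outcome, and no control group would show a similar loss.

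Two conclusions are exposed. The primary safety endpoint includes the absence of any device-related SAE, so a single event settles it. The efficacy test compares a small event count with 20%, so losing one event can matter near the limit. If patients with a failed or painful procedure asked for deletion more often than others, the bias would favour the device. That is plausible, but the documents neither state it nor give a rate.

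**Working it through.** **Inputs.** Null rate 20% (8.1); planning rate 10.1%, alpha 5%, 85 evaluable and 95 enrolled (8.2); exact binomial test, one-tailed (8.4); looks at 38 and 57 patients (8.4.2); safety endpoint of no device-related SAEs and efficacy target of at most 10% incomplete (3.1).

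**The plan's own figure.** The one-sided normal approximation n = [(1.645·√(0.2·0.8) + 0.842·√(0.101·0.899)) / (0.20 − 0.101)]² gives 84.8, rounded up to 85; 85/0.90 gives 95 after rounding up. The stated sizes reproduce.

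**Limits of the exact test.** Success requires P(X ≤ k | n, 0.20) ≤ 0.05. The largest passing counts are 3 of 38 (p = 0.039), 6 of 57 (p = 0.045), 10 of 85 (p = 0.033) and 12 of 95 (p = 0.042).

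**Deleting one event patient.** Numerator and denominator both fall by one.

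| Before | p | After | p | Result changes? |
|---|---|---|---|---|
| 4/38 | 0.099 | 3/37 | 0.045 | yes |
| 7/57 | 0.093 | 6/56 | 0.051 | no |
| 11/85 | 0.063 | 10/84 | 0.037 | yes |
| 12/85 | 0.108 | 11/84 | 0.069 | no |
| 13/95 | 0.075 | 12/94 | 0.047 | yes |

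At the second look the result would change only if the empty place were filled by a patient without an event (6/57, p = 0.045). Against the 10% target in 3.1, 9/85 (10.6%) becomes 8/84 (9.5%), and 10/95 (10.5%) becomes 9/94 (9.6%).

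**How often the count is one above the limit.** P(X = 11 | 85) is 9.0% at a true rate of 10.1% and 3.0% at 20%. P(X = 13 | 95) is 6.4% and 3.2%.

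**Type I error under assumed deletion rates.** Let X ~ Bin(n, 0.20), let each event patient have data deleted with probability q, and assume no deletions among other patients (the unfavourable case). Single final look:

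| q (assumed) | n = 85 | n = 95 |
|---|---|---|
| 0 | 3.3% | 4.2% |
| 2% | 4.0% | 5.0% |
| 5% | 5.3% | 6.0% |
| 10% | 7.9% | 7.9% |
| 20% | 14.6% | 15.4% |

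**Safety endpoint.** One device-related SAE in 95 patients fails it. If that patient is dropped, the count is 0 in 94 and the endpoint is met.

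**With a counting rule.** If a deleted patient stays in the denominator and unknown completion counts as incomplete, 11/85 stays 11/85 (p = 0.063), and the single-look error is no higher than 3.3% (n = 85) or 4.2% (n = 95).

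**The case against.** The strongest reply is that the plan holds more safeguards than the deletion clause suggests.

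- Section 5.4 continues safety and efficacy collection after a post-procedure withdrawal. This stands as evidence that the section contradicts itself. It does not say that the collected data survive a deletion request.
- A reader might infer that an SAE could vanish altogether. The documents do not support that. Section 7.2.4 requires entry within 24 hours, sponsor assessment, and reporting to the ethics committee and competent authority, so a trace remains outside the analysis dataset. What is missing is a statement that the reported event still counts towards the endpoint.
- A reader might infer that the ITT set can hold only patients whose data still exist. Section 8.4.1 does not say so. Section 4.4 keeps enrolment logs and does not re-use patient numbers, so membership can be traced. Only the classification is undefined.
- Section 9.1 allows destruction with the sponsor's written approval, and the audit trail in 9.2.2 is a safeguard. Neither is a clear conflict. The real tensions are within 5.4, and between it and 4.5 and 9.1.3.
- Section 8.4 leaves technical detail to an analysis plan to be finalised before database lock. That gives the missing rule a place but does not supply it.
- Whether the deletion option can be withdrawn depends on consent and data-protection rules in three countries, which the documents do not give. This stands and limits the remedy.

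**Conclusion.** The point holds in a limited form. Followed as written, the plan lets a known event leave the single-arm analysis, and no rule brings it back. That is decisive for the safety endpoint if the only device-related SAE is dropped.

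For efficacy, a reader might infer that one deletion generally decides the trial. It does so only when the count is exactly one above the limit. Under the planning rate that has probability 9.0% at n = 85 and 6.4% at n = 95, and at the second interim look one deletion alone is not enough.

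The error rates above rest on an assumed deletion rate among event patients and none among others, for a single final look. The expected frequency is probably low, but that too is an assumption. The rule should be changed because it leaves a route to reversing a primary endpoint uncontrolled and is cheap to close.

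**What to change.** 1. In 5.4, make retention of data collected up to withdrawal the rule as far as applicable law allows, and say so in the consent form. Reconcile the section with its own continued collection after the procedure, with 4.5 and with 9.1.3.
2. Where erasure is required after Endorail was started, keep the patient in the ITT denominator, using the enrolment log or, if permitted, an unidentified tally of completion and SAE status.
3. In the efficacy analysis, at the interim looks as well as the end, count completion as incomplete if it is no longer known.
4. State that a device-related SAE already reported under 7.2.4 still counts towards the safety endpoint. Do not presume an SAE for a deleted patient with none reported; otherwise one privacy request would fail that endpoint.
5. Report the number of deletions.

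The cost is a protocol and consent-form change needing ethics approval (9.5.1, 9.6.1) and a few lines in the analysis plan. Patients lose the deletion option where the law does not require it, and the reported event rate may be slightly less favourable.
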